1.3.2 Secondary efficacy endpoints

The secondary efficacy endpoints are:

- Change in IOP from baseline to Week 12 at three time points (08:00, 10:00 and 16:00) in the contralateral eye
- Change in IOP from baseline to Week 6 at three time points (08:00, 10:00 and 16:00) in the worse eye and in the contralateral eye
- Efficacy assessed by the investigator at Week 6 and Week 12

1.3.3 Safety endpoints

Safety and tolerability endpoints are:

- Conjunctival hyperaemia on McMonnies scale in each eye at Week 6 and Week 12
- Change from baseline of conjunctival hyperaemia on McMonnies scale in three classes (improvement, no change, worsening) at Week 6 and Week 12
- Score of each ocular symptom throughout the day and the sum of these scores
- Score of each ocular symptom upon instillation and the sum of these scores
- Score of each ocular sign
- Corneal fluorescein staining (CFS) on Oxford scale
- Far Best Corrected Visual Acuity expressed in LogMar
- Ocular tolerance assessed by the investigator
- Ocular tolerance assessed by the patient
- Ocular and systemic adverse events (AEs) by System Organ Class (SOC) and Preferred Term (PT)

1.4 Study treatments

1.4.1 Treatment groups

Run-in treatment/wash out

There is one run-in treatment with the following dose regimen:

- Azopt®: a preserved brinzolamide 10mg/ml eye drops suspension in 5 mL multi-dose container. It is a white to off-white suspension

During the run-in period, the patient should instill one drop in each eye twice a day, morning and evening for 5 weeks. The Azopt® treatment must be stopped 2 weeks or 1 week before the randomisation visit (respectively before or after Clinical Study Protocol amendment 1 – 05JUL2019).

Treatment period

There are two groups of treatment with the following dose regimen:

- T4032: a preservative-free bimatoprost 0.01% eye drops gel in single-dose container. It is a sterile, colourless and opalescent gel

- Lumigan® 0.01%: a preserved bimatoprost 0.1 mg/ml eye drops solution in 3 mL multi-dose container. It is a colourless solution

At the randomisation visit, the patient was randomly assigned to receive T4032 or Lumigan® 0.01%. The patient should instil one drop once daily at 20:00 (± 1 hour) in the conjunctival sac of each eye for 12 weeks.

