PROTOCOL SYNOPSIS

Title	Efficacy and safety assessment of T4032 (unpreserved bimatoprost 0.01%) versus Lumigan® 0.01% in ocular hypertensive or glaucomatous patients.
Sponsor	Laboratoires THÉA
EudraCT-Number	2017-000846-23
Sponsor Study No.	LT4032-301
International Coordinator	
Study Centres	This international study is planned to be carried out at approximately 130 sites spread over 15 to 25 countries.
Planned Schedule	Planned initiation: October 2018 Planned last patient last visit: December 2020
Study Phase	Phase III
Primary Study Objective	To demonstrate the non-inferiority of T4032 unpreserved eye drops compared to Lumigan® 0.01% in terms of efficacy.
Secondary Study Objective(s)	To evaluate the safety and efficacy of T4032 versus Lumigan® 0.01%.
Sample Size	360 evaluable patients Accounting for a 10% drop-out/non evaluable rate, 400 initially treated patients are expected to be randomised. Number of screened patients will depend on the screen failure rate and is estimated at 668 patients.
Study Design	International, multicentre, randomised, 2 parallel groups, investigator-masked, 3-month treatment. 4 visits: 
• Visit #1: Day -49 ± 3 days (Screening Visit)• Visit #2: Day 1 (Randomisation Visit)• Visit #3: Week 6 (Day 42 ± 3 days)• Visit #4: Week 12 (Day 84 ± 7 days) (Final visit)• Follow-up phone call: Week 16 (Day 112 ± 7 days) Run-In/Wash-Out: Patient must be willing to discontinue her/his current treatment for 7 weeks ($49 \text{ days} \pm 3$ days) prior to the randomisation visit, in order to determine the IOP eligibility. Patient must follow a run-in period with only brinzolamide eye drops (Azopt®), one drop in each eye twice a day (morning and evening) for 5 weeks.

	The Azopt® treatment must be stopped for 2 weeks prior to the randomisation visit.
Study Duration	23 weeks total of study duration: 5 weeks of run-in + 2 weeks of wash-out 12 weeks of treatment duration 4 weeks of follow-up.

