1.2.2 Schedule of assessments and study procedures

All patients are expected to attend 4 visits at the investigator centre during the course of the study followed by a phone call:

- Visit #1: Day -42 or Day -49 ±3 days (Screening Visit) (respectively before or after Clinical Study Protocol amendment 1 – 05JUL2019)
- Visit #2: Day 1 (Randomisation Visit)
- Visit #3: Week 6 (Day 42±3 days)
- Visit #4: Week 12 (Day 84±7 days) (Final Visit)
- Follow-up phone call: Week 16 (Day 112±7 days)

FLOW CHART: Schedule of visits and procedures

	Visit# 1 Screening Visit Day -42 or Day -49* (± 3 days)	14 or 7 days before visit#2*	Visit# 2 Randomisation Visit Day 1	Visit# 3 Day 42 (± 3 days) Week 6	Visit# 4 Final Visit or premature discontinuation visit Day 84 (± 7 days) Week 12	Follow-up Phone call Day 112 (± 7 days) Week 16
Informed consent	X					
Demography	X					
History of glaucoma or ocular hypertension	X					
Ocular medical and surgical history (other than the studied disease)	X					
Systemic medical and surgical history	X					
Previous and concomitant ocular/non ocular treatments	X					
Ocular symptoms throughout the day ⁽¹⁾	X					
Ocular symptoms upon instillation ⁽¹⁾						
Far Best Corrected Visual Acuity (BCVA)	X					
Intra-Ocular Pressure (IOP) assessment ⁽²⁾	X					
Fundus examination	X ⁽³⁾					
Central corneal thickness measurement	X ⁽³⁾					
Automated visual field	X ⁽³⁾					
Slit lamp examination ⁽⁶⁾	X					
Corneal fluorescein staining (Oxford grading scheme)	X					
Conjunctival hyperaemia (McMonnies scale)	X					
Pregnancy test ⁽⁷⁾	X					
Adverse event (AE)						
Verification of inclusion and exclusion criteria / Patient status	X					
Run-in treatment (Azopt®) dispensation ⁽⁸⁾	X					
Run-in treatment /Wash-out compliance			X			

Randomisation (IWRS)			X					
Investigational Medical Product (IMP) dispensation ⁽⁹⁾			X		X			
IMP (T4032 or Lumigan®) compliance					X		X	
Efficacy assessment by the investigator ⁽¹⁰⁾			X	X		X		
Ocular tolerance assessment by the investigator ⁽¹⁰⁾			X	X		X		
Ocular tolerance assessment by the patient ⁽¹⁰⁾			X		X		X	

*Respectively before or after Clinical Study Protocol amendment 1 – 05JUL2019

In case of premature discontinuation during the run-in/wash-out period or patient non-eligibility at visit#2, the investigator must perform the evaluations described for the randomization visit (visit #2) except to IOP measurements at 10:00 and 16:00, pregnancy test, randomization and IMP dispensation.

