All the ocular assessments have to be performed in both eyes.

- (1) Ocular symptoms (irritation/burning, stinging, itching, tearing, eye dryness feeling, foreign body sensation), scored using 0-3 scale, will be collected by the investigator /delegate.
- (2) At Screening Visit, one IOP measurement should be performed at 08:00 (\pm 30 minutes). At Day 1, Day 42/Week 6 and Day 84/Week 12, IOP should be measured at three time points: 08:00, 10:00 and 16:00 (each \pm 30 minutes) with a.m. measurements of IOP at least 2 hours apart. IOP measurements should be done at the same hours (\pm 30 min) than Day 1, by the same investigator and using the same technique (Goldmann applanation tonometer) for all visits.
- (3) To be performed if fundus examination / central corneal thickness measurement / automated visual field not done within the previous 12 months and/or results dating from the last 12 months not available.
- (4) To be performed only if the IOP is not stable at the Week 12 visit or if the ophthalmologist judges that it is necessary.
- (5) Azopt® must be stopped for 2 weeks before the Randomisation Visit.
- (6) Slit lamp examination: Score of each ocular sign (blepharitis, eyelid oedema, iris pigmentation modification, abnormal eyelashes aspect, folliculo-papillary conjunctivitis or other ocular abnormality) will be recorded in each eye using 0-3 scale.
- (7) Urinary test to be done for childbearing potential women.
- (8) Run-in treatment (Azopt®) will be instilled by the patient one drop in each eye twice a day (morning and evening) for 5 weeks.
- (9) One drop of IP (T4032 or Lumigan®) will be instilled by the patient in each eye once daily at 20:00 (\pm 1 hour) for 12 weeks.
- (10) Efficacy and ocular tolerance will be assessed by the investigator and the patient as very satisfactory, satisfactory, not very satisfactory, or unsatisfactory.
- (11) In case of AE, all treatments of the follow-up period will be collected.

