4.3.8 Compliance of Azopt®

Compliance of Azopt® will be calculated for the worse eye and the contralateral eye separately.

Compliance of Azopt® (%)

Compliance of Azopt® will be calculated for each eye as follows:

(Actual number of instillations of Azopt®) / (Theoretical number of instillations of Azopt®) x 100 with:

- Theoretical number of instillations of Azopt® = (Date of randomisation visit – 8 or – 15 (respectively before or after Clinical Study Protocol amendment 1 – 05JUL2019 based on the recorded information on the e-CRF) – Date of screening visit + 1) *2, (*2: as patients should instil one drop twice a day in each eye)
- Maximum number of instillations of Azopt® = (Date of last instillation – Date of first instillation + 1) *2, as patients should instil one drop twice a day in each eye
- Actual number of instillations:
 - If no change in Azopt® instillation is recorded in the e-CRF, the actual number of instillations will be considered as equal to the maximum number of instillations
 - If changes in Azopt® instillation are recorded in the e-CRF, the actual number of instillations will be equal to:
(Date of last instillation – Date of first instillation + 1) *2
– [$(\sum$ Number of days with number of instillations per day in the corresponding eye=0 x 2)
+ \sum Number of days with number of instillations per day in the corresponding eye=1)]
+ \sum Number of days x (Number of instillations per day in the corresponding eye when number of instillations is >2 -2)

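### Do the reversed before/after-amendment wash-out lengths in the SAP put the per-protocol set or the run-in compliance results at risk?

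*SAP*

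**What the plan says.** The SAP states the length of the Azopt-free period in four places.

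- Section 1.4.1: treatment "must be stopped 2 weeks or 1 week before the randomisation visit (respectively before or after Clinical Study Protocol amendment 1". Read in order, this is 2 weeks before the amendment and 1 week after.
- Section 1.2.2, flow-chart column header: "14 or 7 days before visit#2", with an asterisk explained as "respectively before or after Clinical Study Protocol amendment 1 – 05JUL2019". This is the same order as section 1.4.1.
- Section 1.2.2, footnote 5: "Azopt® must be stopped for 2 weeks before the Randomisation Visit", with no split by amendment.
- Section 4.3.8, theoretical number of Azopt drops: "Date of randomisation visit – 8 or – 15 (respectively before or after Clinical Study Protocol amendment 1 – 05JUL2019". This is the shorter offset before the amendment and the longer one after.

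Section 1.2.2 also gives the screening visit: "Visit #1: Day -42 or Day -49 ±3 days (Screening Visit) (respectively before or after Clinical Study Protocol amendment 1". Section 1.4.1 sets the Azopt run-in at 5 weeks for everyone.

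The protocol synopsis (Study Design) has screening at Day -49, 5 weeks of Azopt, and "The Azopt® treatment must be stopped for 2 weeks prior to the randomisation visit". The SAP introduction says that it is based on protocol version 3.0 of 05-JUL-2019, the same date that it gives for amendment 1.

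**The concern.** Two statements that both split by amendment give opposite answers, and a third does not split at all. They cannot all be true. The flow chart even disagrees with itself, because its screening and wash-out columns share one before/after footnote yet do not fit together around a 5-week run-in. The ±3-day window on screening does not absorb a 7-day difference.

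The wash-out matters clinically because it precedes the baseline IOP. Statistically, the worry is the per-protocol set. Under section 2.4 that set drops patients with a major violation, and under section 6.1.2 the primary MMRM and both ANCOVAs are repeated in it. In a non-inferiority trial that repeat carries weight. If someone grading deviations took the nominal wash-out from section 1.4.1, each cohort would be held to the other cohort's length. A second worry is run-in compliance, which section 5.3 classes at 80% and 120% and whose denominator depends on the nominal wash-out.

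**Working it through.** **Inputs.** Screening at Day -42 (before) or Day -49 (after), from section 1.2.2. Run-in of 35 days at 2 drops a day per eye, which is 70 drops, from section 1.4.1. Offsets of 8 (before) and 15 (after), from section 4.3.8. The interval from screening to randomisation is taken as 42 or 49 days.

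**Step 1: which order do the visit days support?** Wash-out = screening interval - 35.

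| Cohort | Interval | Implied wash-out | Section 1.4.1 | Run-in left under section 1.4.1 |
|---|---|---|---|---|
| Before | 42 | 42 - 35 = 7 | 14 | 42 - 14 = 28 |
| After | 49 | 49 - 35 = 14 | 7 | 49 - 7 = 42 |

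Neither 28 nor 42 days is 5 weeks, so section 1.4.1 does not fit the SAP's own calendar. The protocol synopsis, with Day -49 and 2 weeks, fits the second row of the implied column.

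**Step 2: does the compliance formula work as written?** Theoretical drops = (interval - offset + 1) × 2.

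- Before: (42 - 8 + 1) × 2 = 70.
- After: (49 - 15 + 1) × 2 = 70.

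Both equal the full 5-week course, so a fully adherent patient scores 70/70 = 100% in either cohort. The formula holds its own offsets and assigns the cohort from the e-CRF. It does not refer to section 1.4.1.

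**Step 3: what if someone put the section 1.4.1 order into that formula?**

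- Before: (42 - 15 + 1) × 2 = 56, and 70/56 = 125.0%, in the class above 120%.
- After: (49 - 8 + 1) × 2 = 84, and 70/84 = 83.3%, still in the 80-120% class.

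The SAP does not make this substitution. Even if it did, not every pre-amendment patient would move. One with 67 drops scores 67/56 = 119.6% and stays in the middle class. One screened 45 days before randomisation, inside the window, has (45 - 15 + 1) × 2 = 62 expected drops and scores 70/62 = 112.9%.

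**Step 4: where does wash-out length enter an analysis?**

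- *Model covariate* (sections 4.3.5 and 6.1.1): randomisation date minus date of last Azopt drop. These are actual dates, so the nominal length is not used.
- *Descriptive split at 8 days* (section 5.2): a cut on duration, not on amendment. Under section 4.3.8 the last expected drop is 8 or 15 days before randomisation. By the section 4.3.5 definition those patients have durations of 8 and 15, one on each side of the cut.
- *Azopt compliance* (sections 4.3.8 and 5.3): sound as written, by step 2, and only described.
- *Per-protocol set* (section 2.4): deviations are deviations from the protocol, listed in a separate document and graded at a blind review before database lock. Section 1.4.1 is not named as the reference, and neither supplied document contains a wash-out deviation rule, a tolerance or a grade.

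**Step 5: could the wording have changed what patients did?** Section 1.5 reports the end of recruitment, with 723 screened and 485 randomised. SAP text written after that cannot have altered any run-in or any baseline IOP.

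**The case for a change.** The best case for acting is that the SAP is the document open on the table at the blind review, and its treatment section is a natural place to look up the wash-out. Section 8 lists changes from the protocol and says nothing about the reversal, so a reader gets no warning. Someone tidying the SAP could also resolve the conflict the wrong way, by editing section 4.3.8 to match section 1.4.1. A post-amendment patient who missed only three drops would then score 67/84 = 79.8% and fall below 80%. A reader of the 8-day split who relied on section 1.4.1 would attach the two strata to the wrong protocol versions.

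What stands is that the contradiction is real, and that the sponsor should make sure the deviation document did not copy the section 1.4.1 order. What does not stand is that the plan, followed as written, gives a wrong result. The effect on the per-protocol set needs two further things that the documents do not show: a deviation rule taken from section 1.4.1, and a major grade for breaching it. The compliance figures need an edit that the SAP does not contain. The tables for the 8-day split are titled by duration and not by amendment, so any misreading is the reader's and the numbers do not change.

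Footnote 5 adds little as a third version. It repeats the footnote in the supplied protocol's schedule, and it is unsplit because that protocol has only one length.

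**Conclusion.** This is a clerical slip: a before/after order in section 1.4.1 and the flow-chart header that is opposite to section 4.3.8 and to the order implied by the visit days, plus a footnote carried over without the split. The conflicting passages must be reconciled with the protocol version in force for each cohort. That is routine correction of descriptive text, and it alters no analysis set definition, model, formula or table.

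Its size in the stated analyses is nil. The m-ITT primary analysis uses actual wash-out dates, and the compliance denominator is 70 in both cohorts. An effect on the per-protocol set remains possible only under the two conditions given above. That set is a secondary population under section 2.4.

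The conclusion rests on two assumptions: that deviations are graded against the protocol, as section 2.4 words it, and that section 4.3.8 is programmed as printed. The protocol in force before the amendment is not among the documents, so the length that applied to that cohort is for the sponsor to confirm. Nothing here says which wash-out is clinically right.

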1.4.2 Randomisation

1.4.2.1 Randomisation procedure

The randomisation code list stratified by site was generated by Aixial. Patients were randomised on a 1:1 basis to T4032 or Lumigan® 0.01%. The investigational medicinal product (IMP) (T4032 or Lumigan®) was allocated to the patients according to randomisation using an interactive web response system (IWRS).

1.4.2.2 Masking

This is an investigator-masked clinical study. The first ophthalmologist investigator should therefore remain masked to the IMP, and not dispense or receive the returned medication from the patients.

Masking is achieved by providing the two IMPs (T4032 and Lumigan® 0.01%) in identical cardboard containers and by identifying each IMP by an IMP number.

The code should not be broken except:

- in case of medical emergency (where knowledge of the IMP received would affect the treatment of the emergency)
- or when it is a regulatory requirement

If an emergency code breaking becomes necessary, the investigator should notify the Sponsor before code breaking. The investigator and/or pharmacist are responsible for accessing the IWRS to obtain the code of the IMP (T4032 or Lumigan®) allocated to the patient. When a code is broken, the date, time and reason must be recorded in the patient's source documentation as well as in the e-CRF, and in any associated Serious AE (SAE) report. The IMP code should not be disclosed in these documents.

During the SAE assessment procedure by the Global Drug Safety & Medical Information Department, the code might be broken for reporting purposes. The relevant THEA, Contract Research Organisation, and investigator staff remains unaware of the identification of the IMP (T4032 or Lumigan®).

The overall randomisation list will only be broken for data analysis after database lock

1.5 Sample size considerations

The sample size determination was based on the primary efficacy endpoint, *i.e.*, the change in IOP at the three time points (08:00, 10:00, 16:00) after 12 weeks of treatment, in the worse eye.

Non-inferiority of T4032 *versus* Lumigan® 0.01% will be tested with a non-inferiority margin of 1.5 mmHg. Non-inferiority will be concluded if it is achieved for each of the three time points 08:00, 10:00 and 16:00.

The evaluation will be based upon a two-sided 95% confidence interval (CI) on the difference in mean change in IOP after 12 weeks of treatment.

With data available for 180 patients in each arm, there is more than 90% power to show that the T4032 unpreserved eye drops is non-inferior to Lumigan® 0.01% preserved eye drops. The hypothesis was based on the 1.5 mmHg margin, assuming no difference between the two groups (average difference of 0 mmHg), and a standard deviation of 3 mmHg and correlation between time-points of 0.7 on the primary efficacy variable.

Evaluable patients are defined as randomised patients having received at least one dose of IMP (T4032 or Lumigan®) and with at least one post-randomisation efficacy assessment.

Accounting for a 10% dropout/non-evaluable rate, 400 initially treated patients were expected to be randomised.

The sample size of 400 randomised patients is also justified to collect enough safety data. Number of screened patients depends on the screen failure rate and was estimated at 668 patients.

At the end of the recruitment period, 723 patients were screened and 485 patients were randomised.

2 ANALYSIS SETS

The following analysis sets will be considered.

2.1 Safety set and Azopt® Safety Set

The Safety set will include all enrolled patients, having received at least one dose of IMP (T4032 or Lumigan®) and considered as-treated. Safety endpoints will be analysed on the Safety set.

The Azopt® Safety set will include all enrolled patients, having received at least one dose of Azopt®.

Note: Enrolled patients will be patients who have signed the informed consent and for whom the screening visit has been recorded in the e-CRF.

2.2 Intent-to-treat set

The Intent-to-Treat (ITT) set will include all randomised patients and considered as-randomised (*i.e.*, according to the randomisation at Day 1). The ITT set will be considered as a secondary population and will be used for sensitivity analyses for the primary efficacy endpoint.

2.3 Modified intent-to-treat set

The modified ITT (m-ITT) set will include all randomised patients having received at least one dose of IMP (T4032 or Lumigan®), with at least one baseline and one post randomisation efficacy assessment and considered as-randomised (*i.e.*, according to the randomisation at Day 1). The m-ITT set will be the primary population for efficacy analysis.

2.4 Per-protocol set

The Per-protocol (PP) set will include all m-ITT patients without any major protocol violation. Deviations from the protocol, including violations of inclusion/exclusion criteria will be detailed in a separate document and assessed as “minor” or “major” in cooperation with the Sponsor during a blind review meeting prior to the database lock. The PP set will be considered as a secondary population.

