6 EFFICACY ANALYSIS

The primary efficacy endpoint will be primarily analysed on the m-ITT set. Sensitivity analyses will be performed on the ITT and PP sets. Secondary efficacy endpoints will be analysed on the m-ITT set and on PP set.

For efficacy variables, descriptions will be given by treatment group at each assessment time. Change from baseline will also be presented.

Of note, for analyses on change from baseline in IOP at 10:00 (respectively at 16:00) in the worse eye and in the contralateral eye, the baseline IOP is the IOP recorded at 10:00 (respectively at 16:00) at Day 1, before the first instillation.

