6.1.1 Main analysis of the primary efficacy endpoint

The non-inferiority of T4032 to Lumigan® 0.01% on the change from baseline in IOP will be primarily tested using a MMRM approach. Three independent models will be performed, one for each time point (*i.e.*, at 08:00, 10:00 and 16:00). Each model will include as fixed factors, treatment, scheduled visit time point (Week 6 and Week 12), baseline IOP, wash-out duration, country as covariates, treatment by visit interaction, baseline IOP by visit interaction, and patient as random factor. The Restricted Maximum Likelihood (REML) estimation approach will be used, and the default covariance structure will be unstructured. Consistent with MMRM model fitting, no explicit imputation of missing assessments for a given visit time point will be performed. The 95% CI for treatment effect (difference T4032 - Lumigan® 0.01%) will be estimated at Week 12 in this model. Non-inferiority will be achieved if the upper bound of the 95% CI for the difference between treatment groups (T4032 - Lumigan® 0.01%) is lower than the margin of +1.5 mmHg for each of the three time points 08:00, 10:00 and 16:00.

The syntax with SAS using the MIXED procedure is detailed in [Appendix 1](#).

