6.1.2 Sensitivity analyses of the primary efficacy endpoint

Whilst patients who have missing data at Week 12 but who have an earlier recorded value (*i.e.*, Week 6) will be included in the MMRM primary analysis, the interpretability of the results from the primary model will depend on the missing data satisfying the Missing at Random. To support the validity of the conclusions drawn from this analysis, sensitivity analyses will be performed to explore the dropout pattern and its possible impact on treatment comparisons.

1) Missing values at Week 12 at 08:00, respectively at 10:00 and at 16:00, will be replaced by the post-randomisation last available value (*i.e.*, the Week 6-based IOP, if available) at 08:00, respectively at 10:00 and at 16:00, *i.e.*, based on LOCF method. The change from baseline in IOP at Week 12 will be analysed using an ANCOVA including treatment, baseline IOP, wash-out duration and country. Three independent ANCOVA will be performed, one for each time point (*i.e.*, at 08:00, 10:00 and 16:00). The adjusted mean treatment differences (T4032 - Lumigan® 0.01%) and their corresponding 95% CI will be estimated in these models to test the non-inferiority hypothesis.

2) The same analyses as the ones planned on the post-randomisation last available value will be performed on the observed value at Week 12 (i.e., missing values at Week 12 will not be replaced). The change from baseline in IOP recorded at Week 12 will be analysed using an ANCOVA including treatment (T4032/Lumigan®), baseline IOP, wash-out duration and country. Three independent ANCOVA will be performed, one for each time point (i.e., at 08:00, 10:00 and 16:00). The adjusted mean treatment differences (T4032 - Lumigan® 0.01%) and their corresponding 95% CI will be estimated in these models to test the non-inferiority hypothesis.

The syntax with SAS using the MIXED procedure is detailed in [Appendix 1](#).

The primary analysis (i.e., based on the MMRM approach) and the same sensitivity analyses presented here above will be performed in the ITT and PP sets.

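### The non-inferiority verdict rests on the m-ITT set alone; a per-protocol result that fails the margin would not change it

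*SAP*

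**What the plan says.** SAP Section 2.3 fixes the deciding set: "The m-ITT set will be the primary population for efficacy analysis". A patient enters it after one dose of study product, with a baseline and one later efficacy assessment. Under Section 2.4 the PP set "will include all m-ITT patients without any major protocol violation". Deviations are graded minor or major "in cooperation with the Sponsor during a blind review meeting prior to the database lock", and the section ends: "The PP set will be considered as a secondary population".

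Section 6 repeats the ranking: "The primary efficacy endpoint will be primarily analysed on the m-ITT set. Sensitivity analyses will be performed on the ITT and PP sets". Section 6.1.1 declares success when the upper limit of the 95% CI for T4032 minus Lumigan "is lower than the margin of +1.5 mmHg for each of the three time points 08:00, 10:00 and 16:00". Neither that rule, nor Section 1.5 (sample size), nor Section 3.6 (multiplicity) mentions the PP set.

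The PP work is nevertheless planned in full. Section 6.1.2 says that the primary MMRM and the same "sensitivity analyses presented here above will be performed in the ITT and PP sets". Appendix 2 lists the PP results as Tables 4.13 to 4.15 (MMRM), 4.22 to 4.24 (LOCF) and 4.31 to 4.33 (observed values). The protocol synopsis gives the margin and the three-time-point rule but names no analysis set.

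**The concern.** In a superiority trial, keeping deviators in the analysis usually makes success harder. In a non-inferiority trial it can make success easier, because patients who miss doses, stop early or use other pressure-lowering treatment may look alike in both arms.

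The m-ITT set can contain such patients. Its definition sets no compliance requirement, and Section 5.3 tabulates a class below 80% compliance. Section 4.2 assigns a premature-withdrawal visit to the next scheduled visit regardless of its date, and allows readings taken after treatment stopped if the blind review confirms their use.

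At stake is the case where the m-ITT interval lies below +1.5 mmHg at all three time points and the PP interval does not. As written, the rule calls this non-inferiority. Any other reading of the discordance would have to be argued after the results are known.

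**Working it through.** **Inputs.** From SAP Section 1.5: margin 1.5 mmHg, two-sided 95% CI, SD 3 mmHg, correlation 0.7 between time points, assumed true difference 0, 180 evaluable per arm, 10% drop-out, 485 actually randomised. From Section 1.4.2.1: 1:1 allocation. Expected evaluable patients per arm from actual recruitment: 485 / 2 × 0.9 = 218.

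**The plan's own figures.** With 180 per arm, SE = 3 × √(2/180) = 0.316. Power at one time point is Φ(1.5/0.316 − 1.96) = 99.7%. For all three, from a trivariate normal with correlation 0.7, it is 99.3%. The stated *more than 90%* is therefore true with room to spare; 105 per arm would give 90% jointly. Also 360 / 0.9 = 400, as stated.

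**Dilution model (assumed).** Adherent patients differ by exactly 1.5 mmHg, so a claim would be false. A share f of m-ITT patients are deviators with no difference between arms. The m-ITT difference is then D = 1.5 × (1 − f). With 218 per arm, SE = 3 × √(2/218) = 0.287. The chance of passing one time point is Φ((1.5 − D)/0.287 − 1.96). For example, f = 15% gives D = 1.275 and Φ(0.225/0.287 − 1.96) = 12.0%.

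The verdict needs all three time points, so two scenarios matter:

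| f | D (mmHg) | False claim, all three at the margin | False claim, one at the margin, other two at 0 |
|---|---|---|---|
| 0% | 1.500 | 0.4% | 2.5% |
| 5% | 1.425 | 1.0% | 4.5% |
| 10% | 1.350 | 2.0% | 7.5% |
| 15% | 1.275 | 3.9% | 12.0% |
| 20% | 1.200 | 6.9% | 18.0% |

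With all three at the margin, the joint rate exceeds 2.5% only once f passes about 12% (13% with 180 per arm, 11% with 242). With a single time point at the margin, the other two pass almost surely and give no protection.

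**Milder dilution.** If deviators keep half of the difference, D = 1.5 × (1 − f/2). At f = 10, 15 and 20% the rates are 1.0%, 1.4% and 2.0% (all three at the margin) and 4.5%, 5.8% and 7.5% (one at the margin).

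**Requiring both sets.** This was simulated with the PP set assumed to exclude exactly the deviators. The false-claim rate stays at about 0.4% (all three at the margin) or at most 2.5% (one at the margin) for f from 10 to 30%. With a true difference of 0, joint power is:

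| Excluded from PP | 180 per arm in m-ITT | 218 per arm in m-ITT |
|---|---|---|
| m-ITT alone | 99.3% | 99.9% |
| 10% | 98.6% | 99.6% |
| 20% | 97.3% | 99.1% |
| 30% | 95.0% | 98.1% |

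**The case against.** A reader might infer that the PP set is ignored. The documents do not support that. Section 6.1.2 runs the sensitivity analyses to support the conclusions drawn. PP Tables 4.13 to 4.15 follow the layout of Table 4.7, whose note carries the +1.5 mmHg criterion. Deviations are graded blind and tabulated by arm, so a PP failure would be visible. What is missing is its consequence.

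A reader might also take 12% and 18% as the error rate of the verdict in general. They apply only when one time point is at the margin and the other two show no difference. Requiring all three gives real protection when all are at the margin, up to about 12% dilution.

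The model is also severe. Major deviations include eligibility violations, which need not remove a treatment difference. The list of deviations is in a separate document that is not available here, so neither their number nor their direction of effect is known.

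Finally, PP excludes patients after randomisation and may be biased either way. A mandatory PP pass lets a selected subset overrule the randomised comparison, and a supportive PP analysis with a stated rule for discordance would be defensible. All of this stands as a limit on size. It does not supply the missing rule. Because both sets must pass, bias in PP cannot create a false claim that the m-ITT rule alone would have avoided; it can only cause a false failure.

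**Conclusion.** The point holds: m-ITT alone decides, and a discordant PP result has no stated effect. The possible inflation is moderate. It is 2.0% to 6.9% at 10 to 20% dilution if all three time points are at the margin, against 0.4% undiluted. It is 7.5% to 18% if only one is, against 2.5%. These figures rest on a true 1.5 mmHg difference in adherent patients, none in deviators, SD 3, correlation 0.7 and 218 per arm, and they fall if deviators keep part of the difference. The documents show that a false claim by this route is possible, not that it is likely. They also do not show that choosing m-ITT as the primary set is in itself wrong. This is a cheap improvement that should be made.

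**What to change.** In SAP Sections 3.6 and 6.1.1, state before database lock: *Non-inferiority is concluded only if the upper 95% confidence limit for T4032 minus Lumigan is under +1.5 mmHg at each of 08:00, 10:00 and 16:00, in the m-ITT set and also in the PP set.* No alpha adjustment is needed, because every condition must be met. Sections 2.4 and 6 should then describe the PP analysis of the primary endpoint as part of the decision.

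Only the protocol synopsis is available here. If the full protocol names m-ITT alone, list the change in Section 8 as a departure from protocol; recruitment had already ended when this SAP was written, so the date of the change should be clear.

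The cost is some text and no new data or models. With 180 per arm, the loss of joint power is about 0.7 points with 10% excluded from PP (99.3% − 98.6%), 2.0 with 20% and 4.3 with 30%, still above the stated 90%. The remaining downside is a false failure if exclusions after randomisation bias the PP comparison against T4032.
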